Neuropsychology: Performance on the Effort Expenditure for Rewards Task (EEfRT), and neurocognitive tasks (see below)

Objective 3. Explore the interrelationship among inflammation, altered reward processing as measured by fMRI, and objective and clinical measures of motivation and negative symptoms in patients with schizophrenia.

Hypothesis 3: Decreased neural activation in reward-related regions will mediate the relationship between inflammatory markers, impaired motivation and negative symptoms.

Immune Markers: Peripheral inflammatory markers: plasma CRP, IFN-alpha, IL-6, sIL-6R, IL-10, TNF-alpha, sTNFR 1 and 2, IL-1 beta, IL-1ra, sIL-2R, and MCP-1

Neuroimaging Tasks: resting state scan; fMRI tasks

Behavior: Positive and Negative Symptom Scale (PANSS); Brief Negative Symptom Scale (BNSS); Snaith Hamilton Pleasure Scale (SHAPS); Inventory of Depressive Symptomatology (IDS-SR); Calgary Depression Scale for Schizophrenia (CDSS), Childhood Trauma Questionnaire (CTQ); Motivation and Pleasure Scale (MAPS-SR)

Neuropsychology: Effort Expenditure for Rewards Task (EEfRT), and neurocognitive tasks (see below)

5. Study Design and Methods

Figure 2: Overview of Proposed Study Visits

Screening Visit Between 9:00 am – 12:00pm	Subject arrives at Grady BHC for consenting and MINI diagnostic interview. They will also complete a physical and psychiatric exam, blood sampling for routine labs, CRP, urine drug screen and pregnancy test. All subjects will be eligible to also complete the MMSE, BNSS, WRAT, and MRI safety screen.
Visit 1	Subjects will be eligible to complete the PANSS, behavioral EEfRT, IDS-SR or SHAPS, and other assessments the PI and study staff may choose from other study visits.
Visit 2 9:00 am	Subject arrives at Emory University Hospital ACTSI suite
9:30 am	Blood Sampling
10:00 am	Behavioral Testing
12:00 pm	Lunch
13:00 pm	MRI Scan
14:30 pm	Complete Study
Visit 3	Complete Behavioral Testing

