Visit 2: Visit 2 will be scheduled within 2 weeks (may be extended by 1 week at the discretion of the PI) of Visit 1. Subjects will be brought by taxi, arranged by study staff, to Emory University where they will undergo behavioral assessments, fasting blood sampling, and MRI scan. These assessments will be conducted at one of two sites to be determined by the PI and the study team: either the ACTSI Emory University Hospital Clinical Research Site and complete the MRI scan at the Emory University Hospital BITC Research Scanner, or the Emory University Department of Psychology and their Facility for Education and Research in Neuroscience (FERN). Transportation will be arranged for patients to be picked up at their home or designated location and brought safely to the Emory University campus. During this visit, patients will undergo the following assessments: (1) fasting blood sampling for plasma inflammatory markers (collected between 9:00am and 10:00am to control for circadian variations), PBMCs, induced pluripotent stem cells (iPSCs), immune repertoire sequencing, and optional mRNA gene expression analyses, (2) Urine Drug Screen (THC quantitative test if required) (3) Urine pregnancy test, (4) Optional saliva collection for microbiome analysis, (5) behavioral testing with objective, self-report and clinician-rated assessments, (6) Optional saliva collection for cortisol testing, (7) MRI scan with imaging tasks described below. Patients will not be allowed to smoke or eat at least 1 hour before the scan. Breaks will be allowed throughout the day, and snacks and a standardized lunch will be provided. Taxi service will be arranged to safely transport the patients back to their home. The Calgary Depression Scale for Schizophrenia (CDSS) and the Motivation and Pleasure Scale (MAPS-SR) will also be administered (scales and tasks may not be administered at the discretion of the PI and the study team).

Visit 3: Visit 3 will be scheduled within 72 hours (up to a week per the PI's discretion) of Visit 2. Visit 3 will take place virtually or at one of the following sites; Grady BHC, EUH GCRC, WMRB or FERN. All assessments that have not been completed will be completed at this visit. Alternatively, these assessments can be administered at Visit 1 or 2 at the study staff's discretion, depending on scheduling and the patient's preference.

Assessments include the following:

- (1) CANTAB
- (2) Neurocognitive Battery (described below)

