Specific Aim 2) To determine the impact of IR and inflammation on reward circuits and negative symptoms in patients with schizophrenia, before and after glucose challenge. Participants described in Aim 1 will undergo the following assessments before and after OGTT: 1) Resting-state and task-based fMRI to assess changes in activation of functional connectivity between the ventral striatum and other reward relevant brain regions using targeted and network-based analyses in relation to inflammatory and metabolic markers. 2) clinical and objective assessments of motivation and negative symptoms. Inflammatory versus metabolic responses to OGTT will be examined as predictors and controlled for in the analyses. *Hypothesis 2a:* Peripheral IR will be associated with decreased functional connectivity within reward circuits, decreased ventral striatum activation, and greater motivational deficits/negative symptoms post-OGTT. *Hypothesis 2b:* Inflammation will mediate the effects of IR on reward circuit functional connectivity, as well as changes in motivational deficits/negative symptoms before and after OGTT.

Study design and methods: Participants from Part A will be approached to enroll in this optional study. A new written informed consent will be obtained from all patients before protocol-specified procedures are conducted. The schedule of assessments for the optional OGTT study can be found in Table 5.

Figure 5: Part C OGTT Schedule of Assessments

Procedures	Screening Visit (Grady BHC)*	Visit 1 Pre-OGTT (Emory GCRC/FERN)	Visit 1 Post-OGTT (Emory GCRC/FERN)
Medical Assessments			
Physical Exam	X*		
Concomitant Medications	X	X	X
Adverse Events	X	X	X
Safety Labs**	X	X	
Vital Signs including waist circumference	X	X	X
CRP	X		
Additional Research Blood (immune and metabolic markers)		X	X
MRI Scan		X***	X
Neuropsychiatric Assessments			
Positive and Negative Symptom Scale (PANSS)	X^		
Brief Negative Symptom Scale (BNSS)	X^		
Calgary Depression Scale for Schizophrenia (CDSS)	X^		
Effort-Expenditure for Reward Task (EEfRT)		X	X
Neurocognitive Battery		X	X
Self-Reports/Questionnaires			
Profile of Mood States (POMS)		X	X

*If >6 months

**Safety labs may include complete blood count, urinalysis, urine drug screen, chemistry

***If Part C is completed within 2 weeks of Visit 2 from Part A of the protocol (or at the discretion of the PI), MRI data may be used from part A as pre-OGTT scan and the pre-OGTT MRI may be omitted.

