^ If Part C is completed within 2 weeks of Visit 2 from Part A of the protocol (or at the discretion of the PI), data from these assessments may be used from part A and these may be omitted

Choice of OGTT as a metabolic challenge: We will use the OGTT because 1) responses to OGTT have been shown to be altered in patients with schizophrenia,¹⁴⁴ 2) it is a clinical diagnostic test, not an intervention, that can pull out differences in IR in non-diabetic but at-risk patients with schizophrenia, 2) IR is associated with dyslipidemia and changes in cholesterol,¹⁵¹ and altered OGTT response should be seen in patients with evidence of altered lipid/cholesterol metabolism in these panels, 3) it has been shown to cause changes in measures of brain functional connectivity, due to either leptin signaling or glucose uptake, that is altered in patients with evidence of IR,¹⁵²⁻¹⁵⁵ 4) it stimulates inflammatory responses,^{158,159} allowing us to further probe immune and metabolic interactions, and 5) OGTT has been used to assess psychiatric/behavioral symptoms as they relate to IR in the Grady population through work in the Grady Trauma Project.¹⁵⁶

Participant Selection

Inclusion Criteria: The same inclusion criteria from Part A will be used.

Exclusion Criteria: The same exclusion criteria from Part A will be used with the added criteria of a) diagnosis of diabetes mellitus.

Description of Study Procedures

Optional Study Screening: Subjects who potentially qualify for enrollment in Part C will be approached at the end of Part A. The exclusion of a diagnosis of diabetes will be made by medical history or HbA1C >6.5, both of which are assessed/measured in Part A. Of note, some individuals may qualify for both Parts B and C. If this is the case, subjects will first be offered Part B and then informed about Part C. This visit will occur at Grady BHC, EUH GCRC, WMRB or FERN. Fasting insulin and glucose will be measured to calculate HOMA-IR. CRP, CBC, urinalysis, vital signs, urine drug screen and pregnancy test (for women) will be collected as well to ensure that there are no active infections, active drug use, and/or pregnancy. If it has been >6 months since Part A, HbA1C will also be measured to ensure that the subject does not have diabetes. If >6 months, a physical exam will be repeated as well. If Part C is completed >2 weeks after Part A, the BNSS, PANSS, and

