CDSS will be repeated at this visit. In addition, subjects will also complete the MRI safety screening form again in case anything has changed since Part A. The total burden of the prescreening visit includes approximately ~1-2 hours of informed consent and blood draw (if symptom measurements need to be completed at this visit, the visit will likely be closer to 2-3 hours). Subjects will be compensated \$25 for the prescreening visit.

OGTT Visit 1: Subjects will be invited to participate in Visit 1 after signing informed consent at screening and meeting all inclusion/exclusion criteria. Visit 1 will be scheduled within 10 days (>10 days can be approved at the discretion of the PI) of Screening to ensure stability of CRP measurement (of note, the CRP at screening will not be used in analyses). Subjects will be brought by taxi/ride share (i.e, Uber) to Emory University Hospital at the Georgia CTSA Clinical Research Center (GCRC). All procedures during this visit will occur prior to and following a 75gm oral glucose tolerance test (OGTT).

Subjects enrolled and previously approved by the PI, with a positive UDS for THC will undergo a THC quantitative test. Subjects will undergo blood draw (fasting) for inflammatory and metabolic markers once before OGTT and at 15 min, 30 min, and 1, 2 and 3 hours post-OGTT. Whole blood will also be collected in Tempus Tubes for gene expression analyses at each time point. The following behavioral assessments will be administered pre and post OGTT administration: 1) Effort Expenditure for Reward Task, 2) Profile of Mood States, and 3) Neurocognitive Assessments described below. An MRI scan will be performed at the Emory Department of Psychology Facility for Education and Research in Neurosciences (FERN), where subjects were previously scanned during Part A. Subjects may undergo 1) Resting State fMRI, 2) Task Based MRI using the fMRI EEfRT and MID tasks, 3) DTI. Which of these MRI procedures will be made at the discretion of the PI. Post-OGTT MRI scan will be performed 3 hours after OGTT administration in order to measure reward circuitry at the peak of the inflammatory response. If Visit 1 is scheduled within 2 weeks of Part A from Visit 2, the pre-OGTT MRI scan may be omitted at the discretion of the PI.

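### A post-lunch Part A scan may replace the Part C pre-OGTT scan, so pre-to-post imaging change in those patients cannot be attributed to the glucose challenge alone

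*Combined protocol and SAP*

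**What the plan says.** **The substitution.** Figure 5 (Part C OGTT Schedule of Assessments) schedules an MRI both before and after the OGTT. Its footnote on the pre-OGTT scan states that "MRI data may be used from part A as pre-OGTT scan and the pre-OGTT MRI may be omitted". This applies when Part C follows Part A Visit 2 by no more than 2 weeks, or otherwise at the PI's discretion. The text under OGTT Visit 1 covers the same case: if the visit falls within 2 weeks, "the pre-OGTT MRI scan may be omitted at the discretion of the PI".

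**The Part A scan.** Figure 2 in section 5 (Overview of Proposed Study Visits) places lunch at 12:00 on the Visit 2 day, then "13:00 pm MRI Scan". The Visit 2 text adds "Breaks will be allowed throughout the day, and snacks and a standardized lunch will be provided" and "Patients will not be allowed to smoke or eat at least 1 hour before the scan".

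**The Part C visit.** OGTT Visit 1 begins before the glucose: "Subjects will undergo blood draw (fasting) for inflammatory and metabolic markers once before OGTT". The post-OGTT scan follows 3 hours after the 75 g load.

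**The rationale.** Under Choice of OGTT as a metabolic challenge, one reason given is that "it has been shown to cause changes in measures of brain functional connectivity, due to either leptin signaling or glucose uptake". The same sentence says this response is altered in patients with evidence of insulin resistance.

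**The analysis.** Part C Specific Aim 2 calls for fMRI before and after the OGTT to assess changes. The Optional Study C Aim 2 paragraph of section 7 lists sex, age, race and BMI as covariates to explore. It has no exclusion, indicator or sensitivity analysis for substituted scans. The Power Analysis paragraph calls the analyses relating pre/post-OGTT marker changes to reward circuitry underpowered and exploratory.

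**The concern.** A pre/post challenge design isolates the challenge only if the two measurements otherwise differ as little as possible. A substituted baseline differs from a same-day one in two further ways: it is taken after a meal, and on another day. By the protocol's own reasoning, glucose intake affects the imaging outcome, so the first difference matters. It is also said to act differently by insulin resistance, which is the predictor in Aim 2. The error in a substituted baseline could therefore be related to the predictor and need not be plain noise.

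Substitution is optional, so one analysis may pool two kinds of change score that do not measure the same thing. At stake are the imaging changes of Aim 2, which the protocol intends as preliminary data for future proposals.

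**Working it through.** **1. The plan's own Part C figure.** The only Part C calculation is n = 19 for a correlation of 0.7 at alpha 0.05 with power 0.95. Exact bivariate-normal power, two-sided, is 0.946 at n = 19 and 0.956 at n = 20. The Fisher z formula, ((1.960 + 1.645)/atanh 0.7)² + 3 = 20.3, gives 21. The stated figure is close enough. It covers correlations between inflammatory and metabolic markers, which need no MRI, so it is untouched by this point.

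**2. How long after lunch the Part A functional data are collected.** Figure 2 gives lunch at 12:00 and scanner entry at 13:00. Figure 7 gives approximate times within the session.

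| Event | Minutes into session | Clock time | Minutes after 12:00 |
|---|---|---|---|
| Resting state starts | 18 | 13:18 | 78 |
| First task starts (protocol one / two) | 33 / 48 | 13:33 / 13:48 | 93 / 108 |
| Scanner exit (one / two) | 57 / 72 | 13:57 / 14:12 | 117 / 132 |

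The data thus fall about 80 to 130 minutes after lunch begins. The rule against eating for at least an hour before the scan sits awkwardly with a 12:00 lunch and a 13:00 scan, and may push the scan later. Either way the patient has been fed. Part C itself samples blood from 15 minutes to 3 hours after glucose, so it treats this interval as post-challenge.

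**3. The two contrasts.**
- Same-day baseline: (3 h after glucose) − (before glucose, with a fasting blood draw).
- Substituted baseline: (3 h after glucose) − (about 1 h or more after lunch, another day).

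The second equals the first minus the fed-versus-fasted shift and minus any day-to-day difference. Of the Aim 2 measures that Figure 5 schedules both before and after the OGTT (research blood, EEfRT, neurocognitive battery, POMS, MRI), only the MRI may be borrowed from another day.

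**4. Can substitution happen on the ordinary schedule?** Visit 3 falls up to 3 days after Visit 2. If Part C screening takes place then (an assumption), the 10-day window to OGTT Visit 1 gives 3 + 10 = 13 days, inside 14. With Visit 3 extended to a week, 7 + 10 = 17 days. That is outside the limit, and only the Figure 5 footnote would then permit substitution.

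**5. Effect on the slope against insulin resistance.** Suppose the fed-versus-fasted shift is a + b × IR, and a fraction f of scans is substituted regardless of IR. The expected slope of change on IR is then off by −f × b. With b = 0 there is no slope bias from this source, only extra noise. With b ≠ 0, which is what the protocol's rationale would suggest if a meal acts like the OGTT, the slope is biased. The documents give neither b nor f.

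**6. Illustration for mean change (assumed values, not from the documents).** Take N = 20, no true glucose effect and a shift of d SDs of change. Bias = f × d. Noncentrality = f × d × √20 / √(1 + f(1 − f)d²), with a two-sided 5% t-test on 19 df.

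| d | Half substituted: bias, error rate | All substituted: bias, error rate |
|---|---|---|
| 0.2 | 0.10 SD, 7.1% | 0.20 SD, 13.6% |
| 0.5 | 0.25 SD, 17.8% | 0.50 SD, 56.5% |
| 0.8 | 0.40 SD, 35.1% | 0.80 SD, 92.4% |

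These rows show sensitivity only. A shift of the opposite sign to a real glucose effect could equally hide it.

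**The case against.** The strongest reply is that little rests on these analyses. The Power Analysis paragraph already calls them underpowered and exploratory, and the powered Part C question concerns blood markers. That stands and sets the priority. It does not excuse an avoidable confounder in results meant to support later proposals.

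Other points for the plan also carry weight:
- The protocol calls the pre-OGTT blood draw fasting, not the scan, and the Part C visit timeline is a figure not shown. The scan's fasting state is an inference from its place before the glucose.
- The rationale concerns the OGTT, not a lunch. That a meal shifts connectivity, and differently by insulin resistance, is plausible but unquantified.
- The Magnetic Resonance Imaging section has food and drink in the 2 hours before a scan recorded on a form, so fed scans could be identified. The analysis plan does not use the form, and Figure 5 does not list it.

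A reader might infer three stronger things that the documents do not support:
- **That Hypotheses 2a and 2b both depend on imaging change.** Hypothesis 2a is worded for the post-OGTT state, which the post scan alone can address. In 2b the word changes attaches to motivation and symptoms. Section 7 defines no connectivity change score. Imaging change enters through the Aim 2 text.
- **That all 20 baselines could be replaced with no time limit.** The open-ended waiver is only in the Figure 5 footnote; the OGTT Visit 1 text keeps the 2-week condition. All 20 is a theoretical ceiling.
- **That a substituted change contains no glucose response.** It may contain one, but does not isolate it.

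**Conclusion.** The point holds for pre/post imaging change in patients whose pre-OGTT scan comes from Part A. In them the change cannot be attributed to the glucose challenge alone, may be biased in relation to insulin resistance, and should not be pooled with change from a same-day scan. Each such patient is 1/20 = 5% of the planned Part C sample. The number of patients and the size of the shift are unknown.

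This rests on three things: the Part A scan following the Figure 2 timetable, the pre-OGTT scan sharing the fasting state of the accompanying blood draw, and the protocol's premise about glucose and connectivity extending to a meal. The different day needs none of these.

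The reach is limited to the exploratory Aim 2 imaging changes. Associations using the post-OGTT scan alone, Part C Aim 1 and all of Part A are unaffected. It should be fixed because the remedy is cheap and an omitted baseline scan cannot be recovered.

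**What to change.** Either of two changes is enough:

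1. **Analysis only.** In the Optional Study C Aim 2 paragraph of section 7, state that a Part A scan used in place of the pre-OGTT scan is excluded from every pre/post-OGTT imaging change analysis and used only cross-sectionally. Report how many patients this concerns. This adds no procedure; the cost is fewer change scores in a sample of 20.
2. **Design.** Remove the MRI substitution from the Figure 5 footnote and from OGTT Visit 1, so that the same-day scan already in Figure 5 is always obtained. The roughly 6-hour visit is already described with MRI performed twice. The cost is the scanner time and burden that omission would have saved (the Magnetic Resonance Imaging section gives 60 to 90 minutes per session), in a population whose no-show rates the protocol describes as high.

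If the option stays in any form, reconcile the footnote (within 2 weeks, or at PI discretion) with OGTT Visit 1 (within 2 weeks, and at PI discretion).

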As an amendment to the original protocol, this research also includes computational analysis of language. Recent developments in the automated analyses of language have shown promising findings in identifying computational measures of language to characterize thought disorder in schizophrenia. However, most of the research to date has focused on measure of incoherence and little attention has been paid to other central features of language in schizophrenia such as poverty of content. This additional research protocol aims to measure “semantic density” through the use of machine learning and Natural Language Processing. It also aims to detect latent semantic content reflective of the psychopathology of thought disorder in schizophrenia. The resulting linguistic findings can be potentially analyzed in conjunction with other biomarkers and future findings of the original study.

4. Objectives

Objective 1. Determine the impact of inflammation on reward processing in patients with schizophrenia using functional magnetic resonance imaging (fMRI).

Hypothesis 1: Increased peripheral blood markers of inflammation will be associated with decreased activation of reward-related ventral striatal regions and decreased connectivity between the ventral striatum and medial prefrontal cortex using whole brain analysis.

Dependent variables:

Immune Markers: Peripheral inflammatory markers: plasma CRP, IFN-alpha, IL-6, sIL-6R, IL-10, TNF-alpha, sTNFR 1 and 2, IL-1 beta, IL-1ra, sIL-2R, and MCP-1

Neuroimaging Tasks: Degree of functional connectivity between the striatum and other brain regions on resting state scan (Z scores); performance on fMRI tasks (see below)

Objective 2. Determine the impact of inflammation on objective and clinical measures of motivation and negative symptoms in patients with schizophrenia.

Hypothesis 2: Increased inflammation will be associated with increased impairment in objective and clinical measures of motivation and negative symptoms.

Dependent variables:

Immune Markers: Peripheral inflammatory markers: plasma CRP, IFN-alpha, IL-6, sIL-6R, IL-10, TNF-alpha, sTNFR 1 and 2, IL-1 beta, IL-1ra, sIL-2R, and MCP-1

Behavior: Scores on the: Positive and Negative Symptom Scale (PANSS); Brief Negative Symptom Scale (BNSS); Snaith Hamilton Pleasure Scale (SHAPS); Inventory of Depressive Symptomatology (IDS-SR), Childhood Trauma Questionnaire (CTQ); Motivation and Pleasure Scale (MAPS-SR)

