Power Analysis: For all three specific aims, analyses will be performed on data collected from 100 patients. Given that the primary statistical analyses will be correlational in nature, an N of 100 will be sufficiently powered (>80%) for moderate effect size ($r=0.5$) at an alpha = 0.05, two-tailed.¹¹⁶ All analyses will correlate inflammatory markers with both neuroimaging and behavioral task performance.

For the optional OGTT, to investigate the correlational relationships between inflammatory markers and metabolic markers, a sample size of 19 would be required to find a correlation of 0.7 at an alpha of 0.05 with Power of 0.95 (calculated in G*Power), which suggests that we have adequate power to investigate these primary relationships both before and after OGTT challenge. However, we are underpowered to identify relationships between changes in inflammatory and metabolic markers pre- and post-OGTT with reward circuitry or motivational deficits. These analyses are thus exploratory and will serve as preliminary data for future research proposals.

Interim Monitoring and Early Stopping:

Subjects will receive a physical examination at Part A Screening or Visit 1. Subjects will also receive safety laboratory testing as well as pregnancy (if female) and substance abuse testing at the Part A Screening or Visit 1, in addition to at Part A Visit 2.

The following events are considered sufficient reasons for discontinuing a subject from the study:

- An adverse event (AE) that, in the judgment of the investigator, may cause severe or permanent harm
- A clinical finding, such as an untreated medical condition, from safety labs or the history and physical examination
- Subject withdraws consent

- Subject lost to follow-up
- Pregnancy
- Protocol violation
- Substance abuse
- Death

Study:

If more than two individuals experience a reportable serious adverse event related to study procedures within a six-month period, the study will be stopped and reviewed by the DSMB.

Analysis Plan and Statistical Methods:

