Region of Interest (ROI) seed placement and connectivity analysis: 8 basal ganglia seeds (4 per hemisphere) will be used representing regions of the ventral and dorsal striatum as defined in Montreal Neurological Institute (MNI) space. In each hemisphere, seeds will be comprised of a spherical mask with a 6 mm radius centered on the ROI. The ventral striatum will be defined by coordinates ($\pm 14, 5, -4$) from a previous fMRI study in IFN-alpha-treated subjects demonstrating maximal decreases in response to a hedonic reward task. The other 3 regions, ventral rostral putamen ($\pm 20, 12, -3$), dorsal caudate putamen ($\pm 28, 1, 3$), and dorsal caudate ($\pm 13, 15, 9$), will be defined according to Di Martino et al. 2008 and other studies assessing functional connectivity with the striatum,¹¹⁷⁻¹¹⁹ and consistent with identified subdivisions of the striatum. Whole brain, subject-level correlation maps indicating regional similarity with the seed region time series will be generated and Fisher transformed to Z-score maps. To assess significance of correlated activity with each bilateral seed region, I will conduct paired t-tests on participants' Z-score maps. To correct for multiple comparisons, resulting maps will be cluster corrected ($p < 0.05$ whole-brain correction, with a height threshold of $p < 0.001$, uncorrected), using SPM12.

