Objective 2: Descriptive statistics will be used to characterize the mean, standard deviation, and standard error for each of these clinical and behavioral measures. For the EEfRT, proportion of hard-task choices across each level of probability as well as the difference between the proportions of hard task choices in low and high reward probabilities (effort allocation) will be calculated. Lower proportions of hard task choices indicate decreased motivation for monetary rewards. A larger difference in the proportion of hard task choices reflects more effort allocation. Regression analyses will be conducted to examine the relationship between task performance and concentrations of inflammatory markers (beginning with CRP). Regression analyses examining the relationship between changes in functional connectivity (Z scores) obtained using fMRI and changes in behavior and neuropsychological performance will also be conducted. In cases where data are not normally distributed, we will use standard transformation procedures to achieve normality, and/or use non-parametric tests of significance. The same covariates and data reduction strategies described above will be used in these analyses.

Objective 3: Formal mediation analysis will be conducted to assess whether functional connectivity mediates

the relationship between inflammation (as measured by inflammatory marker concentrations – beginning with CRP) and behavior (clinical ratings and objective measures, as described above). Bootstrapping will be used to provide an empirical estimate of the sampling distribution for indirect effects and will be used to generate confidence intervals for the purpose of inferential testing. A model of moderated-mediation will also be tested to assess whether mediation pathways are influenced by the presence of high vs. low baseline inflammation. Path analysis will be implemented using macros developed by Preacher and Hayes (<http://quantpsy.org/medn.htm>), which enable inclusion of covariates as well as possible moderators.

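### Part A designates no primary marker or outcome and specifies no multiplicity adjustment across inflammatory markers or behavioural outcomes

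*Combined protocol and SAP*

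**What the plan says.** Section 7, Power Analysis, bases all three aims on 100 patients ("For all three specific aims, analyses will be performed on data collected from 100 patients"). It describes the main analyses only by type: "Given that the primary statistical analyses will be correlational in nature". The sample is called "sufficiently powered (>80%) for moderate effect size ($r=0.5$) at an alpha = 0.05, two-tailed", which is a statement about one correlation. The scope of testing follows: "All analyses will correlate inflammatory markers with both neuroimaging and behavioral task performance".

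Section 4 lists the markers as "plasma CRP, IFN-alpha, IL-6, sIL-6R, IL-10, TNF-alpha, sTNFR 1 and 2, IL-1 beta, IL-1ra, sIL-2R, and MCP-1", which is 12 if the two TNF receptors are counted separately. The assay description under Laboratory Variables names eight analytes plus CRP, so 9. The behavioural measures for Objective 2 begin "Scores on the: Positive and Negative Symptom Scale (PANSS); Brief Negative Symptom Scale (BNSS); Snaith Hamilton Pleasure Scale (SHAPS" and continue with IDS-SR, CTQ, MAPS-SR, EEfRT and a neurocognitive battery.

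For Objective 2, the analysis plan says "Regression analyses will be conducted to examine the relationship between task performance and concentrations of inflammatory markers (beginning with CRP". It also carries over the covariates and marker data reduction described under Objective 1, without giving a method or the number of variables that will remain.

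The only stated correction concerns the imaging maps: "To correct for multiple comparisons, resulting maps will be cluster corrected". The Objective 1 text also says that the seed-map tests are adjusted for multiple comparisons, without saying over what.

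**The concern.** Objectives 1 and 2 are worded as determinations and carry directional hypotheses. Only Objective 3 is worded as exploration. The same section labels underpowered Part C analyses exploratory, and Part C starts from a composite Z-score. Part A has neither device for its behavioural analyses.

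Without a designated test or an adjustment, any nominally significant pair in the expected direction could be reported as support for Hypothesis 2, and the plan gives no error rate for that claim. The preliminary data in section 3 show how this can happen. Eight cytokine-symptom correlations in 10 patients, with p-values from 0.006 to 0.047 and no adjustment mentioned, are summarised as showing the predicted relationship.

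**Working it through.** **1. The plan's own figure.** Fisher z power for one correlation is Φ(atanh(r)·√(N−3) − z₀.₉₇₅). With r=0.5 and N=100 this is Φ(0.5493 × 9.849 − 1.960) = Φ(3.45) = 99.97%. The stated power above 80% is therefore correct for a single test. The smallest r detectable with 80% power is tanh((1.960 + 0.842)/9.849) = 0.28.

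**2. Inputs for the multiplicity check.**
- Markers: the 9 in the assay description.
- Core outcomes: 5 (PANSS, BNSS, SHAPS, MAPS-SR and EEfRT as one measure).
- Wider set: 10, adding IDS-SR, finger tapping, CANTAB reaction time, Trail Making A and Digit Symbol. CTQ is left out because it records past exposure.
- N=100, each correlation tested at two-sided 0.05, no true effects. Testing the full grid at 0.05 is an assumption.
- Correlation among markers, and among outcomes: the documents give none, so a common value from 0 to 0.7 is assumed in both sets.

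**3. Formulas.** Expected false positives = 0.05 × number of tests, whatever the correlation. If tests are independent, the chance of at least one is 1 − 0.95^m, or 1 − 0.975^m counting only the predicted direction. For correlated sets the chance comes from simulating the marker-by-outcome grid.

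**4. Results** (ranges run from correlation 0.7 to 0).

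| Tests | Expected false positives | At least one, either direction | At least one, predicted direction |
|---|---|---|---|
| 9 × 5 = 45 | 2.25 | 51–91% | 25–69% |
| 9 × 10 = 90 | 4.5 | 64–99% | 34–90% |
| CRP × 5 | 0.25 | 15–22% | 8–12% |

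Closed-form checks at independence: 1 − 0.95^45 = 90.1% and 1 − 0.975^45 = 68.0%; 1 − 0.95^90 = 99.0% and 1 − 0.975^90 = 89.8%; 1 − 0.95^5 = 22.6% and 1 − 0.975^5 = 11.9%. These agree with the simulated upper ends to within about a percentage point. One pre-specified test would give 5% and 2.5%.

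**5. Sensitivity to the marker list.** With the 12 markers of section 4 and 10 outcomes (120 tests), 6.0 false positives are expected and the either-direction chance is 71% to 99.8%. The two marker lists differ, so the size of the family is itself not fixed.

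**The case against.** The strongest reply is that the plan is more focused than a full grid. Enrolment is balanced on CRP at 3 mg/L, marker regressions start with CRP, and Hypothesis 1 names ventral striatal activation and ventral striatum-medial prefrontal connectivity in advance. Data reduction is planned for collinear markers and could shrink the marker dimension. The outcomes overlap, which lowers the chance of at least one false positive. Results in the wrong direction would contradict Hypothesis 2, so counting both directions overstates the harm.

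Much of this stands, and it is why the calculation extends to correlation 0.7, itemises the outcomes and shows the predicted direction separately. It does not close the gap. No rule says what follows if CRP succeeds or fails, and CRP alone still meets several outcomes. Data reduction applies to analyses that combine markers, alongside regressions on individual markers; it does not reduce the outcomes or allocate alpha.

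A reader might infer that a false positive is close to certain. That needs the full grid, no true effects and weak to moderate correlation, and the documents state neither the grid nor any correlations. A reader might also infer that nothing corrects across seeds. The documents do not support that flat statement, because the seed-map tests are said to be adjusted and the scope is unclear.

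**Conclusion.** The point holds for Part A: there is no designated primary marker or outcome, and no stated adjustment across markers or behavioural outcomes. If the 45 core pairs were each tested at 0.05, the chance of a false positive would be about 51% to 91%, or 25% to 69% in the predicted direction, against 5% and 2.5% for one pre-specified test. These figures rest on N=100, no true effects, an inferred grid and assumed correlations of 0 to 0.7. They illustrate the exposure that the plan leaves open; they do not predict the trial's error rate. The lack of a designation and of a behavioural adjustment is certain from the text, while the size is conditional. No figure here concerns the imaging maps. The plan should be changed before analysis.

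**What to change.** Before analysis, amend section 7 as follows.

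- Name plasma CRP as the primary exposure. It should be the Visit 2 measurement, since the protocol excludes the screening CRP from data analysis.
- Name one primary outcome for Objective 1, for example ventral striatum-medial prefrontal connectivity, and one for Objective 2, for example BNSS total. Test each at two-sided 0.025.
- Label every other marker-outcome pair secondary and control these with a false-discovery-rate procedure within each objective.
- Settle whether 9 or 12 markers are analysed, list the outcomes that form each family, define the data-reduction method, and say whether the imaging adjustment spans the seeds.

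This is a change of wording, with no new patients or procedures. The price is a slightly larger detectable correlation: tanh((2.241 + 0.842)/9.849) = 0.30 at alpha 0.025, against 0.28 at 0.05, both at 80% power and N=100. Both are well below the planned r=0.5.
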